9.4 Adverse Events (AEs)

Adverse events will be recorded in accordance with UH Bristol's Research Safety Reporting SOP and standard national regulatory requirements.

9.5 AE Definitions

Adverse Event (AE)

"Any untoward medical occurrence in a patient or clinical trial subject administered a medicinal product and which does not necessarily have a causal relationship with this treatment"

Adverse Reactions (ARs)

"All untoward and unintended responses to an investigational product related to any dose administered"

Serious Adverse Event (SAE)

"Any untoward medical occurrence or effect that at any dose results in death, is life – threatening, requires hospitalisation or prolongation of existing hospitalisation, results in persistent or significant disability or incapacity or is a congenital anomaly or birth defect."

Unexpected Adverse Reaction (UAR)

"An adverse reaction, the nature or severity of which is not consistent with the applicable product information (e.g. investigator's brochure for an unauthorised medicinal product or summary of product characteristics for an authorised product)"

9.5.1 Assessment of causality

1. **Not related** – temporal relationship of the onset of the event, relative to the administration of the product, is not reasonable or another cause can by itself explain the occurrence of the event.
2. **Unlikely**
3. **Possibly related** – temporal relationship of the onset of the event, relative to administration of the product, is reasonable but the event could have been due to another, equally likely cause.
4. **Probably related** – temporal relationship of the onset of the event, relative to the administration of the product, is reasonable and the event is more likely explained by the product than by another cause.
5. **Definitely related** – temporal relationship of the onset of the event, relative to the administration of the product, is reasonable and there is no other cause to explain the event or a re-challenge (if feasible) is positive.

Of the above definitions,

"possibly", "probably" and "definitely" related to an investigational medical product are considered adverse reactions "unlikely" and "not related" do not qualify as a causal relationship.

The severity and causality of a serious adverse event, adverse event or SUSAR (Suspected Unexpected Serious Adverse Reaction) should be assessed by a qualified medical practitioner, usually (but not always) the Chief Investigator (CI).

Adverse events or reactions that are not life threatening and do not result in death or hospitalisation may also be considered serious if they jeopardise the subject or require intervention.

All adverse events must be reported to the sponsor immediately, unless they are identified as not requiring this in the trial protocol. It is then the responsibility of the sponsor to report the incident to the MHRA.

9.6 AE Classification

The Investigator(s) will establish the causality of AEs.

9.7 AE Recording

All Adverse Events volunteered by study Patients or elicited by the Investigator must be recorded on the AE forms provided. All AEs must be recorded whether or not considered drug / treatment related.

9.8 AE Reporting

The Investigator must report by telephone all serious AEs to the Sponsor immediately upon discovery, and forward the completed AE form as soon as it is available. If the event has been classified serious / severe, or there is any suspicion

Neonatal Xenon Breathing Device: CoolXenon3 Study	Protocol	CI/2013/4414
	Version	Issue 2, Revision 3
	Issue Date	18 Sept 2019
	Page	45 of 79

that the AE was caused by a test article, details of medical history, concomitant medication and an assessment of compliance with therapy should accompany the AE form. The Investigator must also report the resolution reported AEs promptly.

Non-serious AEs should be reported at the next routine contact.

The time period allowed for reporting such events to the MHRA are as follows:

Reaction which is fatal or life threatening, as soon as possible but no later than 7 days after first occurrence

Reaction which results in hospitalisation /disability/congenital anomaly, as soon as possible, but no later than 15 days after first occurrence

9.9 Reporting Responsibilities to Regulatory Authorities, Investigators and Ethics Committees

The study will be performed subject to Research Ethics Committee (REC) approval, including any provisions of Site Specific Assessment (SSA), and local Research and Development (R&D) approval. The Sponsor will send appropriate safety notifications to regulatory authorities in accordance with applicable laws and regulations.

The Investigator must comply with any applicable site-specific requirements related to the reporting of SAEs involving his/her subjects to the REC that approved the trial.

In accordance with ICH GCP guidelines, the Sponsor will inform the Investigator of “findings that could adversely affect the safety of subjects, impact the conduct of the trial or alter the REC approval to continue the trial”.

10.0 Data Analysis and Statistical Plan

10.1 Statistical Analysis

This is a prospective randomised comparative outcome study. Data presentation will include descriptive statistics only. These will be compared in the 2 treatment groups but also to recordings of the same variables in a similar group of 45 infants (recruited to cooling only from the same entry criteria) recently treated in our department (historical control data). Differences between the groups will be estimated

Sample size is 26 infants in each group. The advisory statistician for this study is [name] who has also advised on all aspects of the Xenon work (pre-clinical and clinical) undertaken to date.

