Therefore, in CoolXenon3 we will record all the same data as in CoolXenon2 and we will use Bayley III converted to Bayley II as appropriate.¹¹ The Bayley clinical neurodevelopmental examination at 18months of age is the primary outcome measure. In the standard treatment, all cooled babies currently undergo MRI brain assessment between 7-10 days of life to confirm the diagnosis of HIE by demonstrating the brain lesions consistent with hypoxia-ischaemia and to prognosticate long-term outcome for parents. In routine clinical practice, some of the cooled babies undergo MRI brain examination around 48 hours of life, when there are concerns of poor recovery of aEEG and abnormal neurology to estimate the severity of brain injury. Undertaking MRI brain assessment around 48 hours of age for all babies during cooling in both cooling and xenon+cooling arms of the study (after completion of xenon) will offer valuable data including early predictors of long-term outcome, assessing the severity of brain injury and progression of brain injury and early effect of xenon on brain injury. Our team is very experienced in looking after the cooled babies during transport and MRI examination. Other putative short-term predictors will continue to be recorded as secondary outcomes. With this enhanced dataset we will be able to validate any early predictors in infants cooled early with or without added Xenon.

There have been no technical problems due to the breathing system, use of the Xenon gas, nor any adverse effects related to these in any of the human studies we have conducted to date.

The safety of Xenon for the immature brain has been demonstrated by no increase in apoptosis³⁰ after 24 hours of breathing the gas in a neonatal piglet model; in comparison breathing isoflurane for the same duration resulted in a 10x increase in apoptotic cell death

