3.3 Secondary Endpoint

The following potential predictors of outcome will be used:

- a. Time to recovery after birth of a normal aEEG¹
- b. MRI scan around 48hours and around day 7 of life, to assess lesions consistent with hypoxic-ischaemia,² absolute quantification of thalamic NAA and white matter fractional anisotropy using tract based spatial statistics.^{3,4,35}
- c. Peak LDH value within 72h of life^{5,36}
- d. Resistance Index (RI).

We will also collect data on:

- e. Plasma glucose at birth (in cord blood)
- f. Age in hours after birth when plasma lactate has fallen to 5mmol/L
- g. Different inotropic drugs needed and the total duration in hours of any inotropic support

Neonatal Xenon Breathing Device: CoolXenon3 Study	Protocol	CI/2013/4414
	Version	Issue 2, Revision 3
	Issue Date	18 Sept 2019
	Page	21 of 79

- h. Number of anticonvulsants given
- i. Amount and duration of sedation (e.g. plasma morphine level), stress level (plasma, salivary, urine cortisol level and adrenocorticotropic hormone)
- j. Age at full oral feeds (breast or bottle or tube)
- k. Neonatal hearing screening result before 14 days of life
- l. Clinical examination at birth, at 7 days of age and at discharge including weight and head circumference

Neurodevelopmental follow up is a part of the routine follow up of infants with HIE, Bayley III examination at 18 months of age.

Disability will be defined as any of:

- m. Bayley III Cognitive Composite score less than 85.¹¹
- n. Bayley III Motor Composite score less than 85 (Bayley scores will also be expressed as a Developmental Quotient (DQ) calculated from developmental age scores as this allows a larger range of scores for those functioning at a low level)³⁷
- o. Bilateral cortical visual impairments
- p. Hearing loss needing amplification > 40dB.

In addition any Adverse Events will be recorded and criteria have been devised for stopping the study early if necessary. The IDRG will review data when 8, 16 and 24 infants have undergone Xenon treatment.

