4.4.1 Specific clinical management of cooling group

This group will be cooled according to the normal protocols of the hospital as this is standard treatment. In standard care, some of the cooled babies will undergo MRI brain assessment around 48 hours of life in addition to the routine MRI brain assessment around 7 days of life, to provide early information about severity of brain injury. In the study, all the babies will undergo MRI brain examination around 48 hours of age. At this time point the babies will be continuing the cooling therapy. Our team is experienced in looking after the cooled babies during transport and MRI examination with least discomfort to the babies. Moreover, all the babies will receive continuous morphine infusion to keep them comfortable during cooling, as part of their standard protocol.

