5. In standard care, some of the cooled babies will undergo MRI brain assessment around 48 hours of life in addition to the routine MRI brain assessment around 7 days of life, to provide early information about severity of brain injury. In the study, all babies will undergo MRI brain examination around 48 hours of life. At this time point, babies will have completed the xenon therapy and will continue with cooling therapy. Babies will be kept comfortable with continuous morphine infusion as per the standard local protocol. Our team is experienced in transporting cooled babies to the MRI and looking after the cooled babies during MR examination. This MRI will provide valuable data regarding the severity of brain injury, early effect of xenon on brain injury and determine the progression of brain injury with xenon+cooling compared with cooling alone.

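### Section 10.1 does not exempt the 48-hour MRI from the comparison with 45 historical cooled infants, although routine care gives that scan only to infants whose recovery causes concern (minor)

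*Protocol*

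**What the plan says.** Section 10.1 plans descriptive statistics only, with differences between groups to be estimated. The two arms are compared with each other and with "recordings of the same variables in a similar group of 45 infants", who are described as "recruited to cooling only from the same entry criteria) recently treated in our department (historical control data". No variable is left out of the historical comparison.

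Section 3.3 lists "MRI scan around 48hours and around day 7 of life" as secondary endpoint b, covering hypoxic-ischaemic lesions, absolute thalamic NAA and white-matter fractional anisotropy.

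On who is scanned at 48 hours, section 2.3 says of routine practice that "some of the cooled babies undergo MRI brain examination around 48 hours of life, when there are concerns of poor recovery of aEEG" and about abnormal neurology. Sections 4.4.1 and 4.4.2 repeat that standard care scans only some infants at this age. For the trial, 4.4.1 says "In the study, all the babies will undergo MRI brain examination around 48 hours of age", and 4.4.2 says "In the study, all babies will undergo MRI brain examination around 48 hours of life". Section 2.3 also says that all cooled infants currently have an MRI at 7-10 days.

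**The concern.** Taken as written, section 10.1 puts the 48-hour MRI variables into the historical comparison. In the trial those variables come from all infants. In the historical group, under the routine practice that the protocol describes, they would come from infants picked out because recovery was poor. Section 1.0 calls the time to recovery of a normal EEG trace the best single early predictor of outcome, so the reason for scanning is itself prognostic.

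Sharing the same entry criteria does not correct this, because the selection happens after entry. Nor is it a matter of drift over calendar time: it would arise even with identical care and case mix in the two periods.

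At stake is how the 48-hour scan is read. Sections 2.3 and 4.4.2 want it to show whether Xenon acts early on the injury. Set against a comparator weighted towards severe injury, both trial arms would look better on this scan for a reason unrelated to treatment.

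**Working it through.** The protocol states no figure on this point, so there is nothing to reproduce. The check is a comparison of texts, followed by an illustration of direction.

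**Who is scanned**

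| Scan | Routine care | Trial |
|---|---|---|
| About 48 hours | Some cooled infants, on concern about aEEG recovery and neurology (2.3; 4.4.1 and 4.4.2 repeat that only some are scanned) | All infants, both arms (2.3, 4.4.1, 4.4.2) |
| About day 7 | All cooled infants, at 7-10 days (2.3) | All infants, around day 7 (3.3) |

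Only the first row differs in who is scanned.

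**Direction**

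Let p be the proportion of infants with a poor outcome, s the probability of a 48-hour scan if the outcome is poor, and u that probability otherwise. Then:

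- share of poor-outcome infants among those scanned = p·s / (p·s + (1 − p)·u)
- number scanned out of 45 = 45 × (p·s + (1 − p)·u)

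If everyone is scanned, the share is p. If s > u, the share exceeds p.

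**Inputs**

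- p: section 2.2 gives local poor-outcome rates with cooling of 39% and more recently 34%, and 48% for the cooled group of the earlier UK trial. Poor clinical outcome stands in here for MRI injury at 48 hours, which is itself an assumption.
- s and u: pure assumptions. The protocol gives no 48-hour scan rate.

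Worked case, p = 0.39, s = 0.8, u = 0.2: share = 0.312 / (0.312 + 0.122) = 0.72; number scanned = 45 × 0.434 = 19.5.

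| Assumed s / u | Share poor, p = 0.34 | p = 0.39 | p = 0.48 | Number scanned of 45 |
|---|---|---|---|---|
| 0.5 / 0.5 (no selection) | 34% | 39% | 48% | 22.5 |
| 0.5 / 0.2 | 56% | 62% | 70% | 13.6 to 15.5 |
| 0.8 / 0.2 | 67% | 72% | 79% | 18.2 to 22.0 |
| 0.9 / 0.1 | 82% | 85% | 89% | 16.7 to 21.8 |

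The first row shows no distortion. If none of the 45 had a 48-hour scan, there would be no comparison to distort. The table therefore establishes the direction whenever s > u. Its sizes only restate the assumed probabilities and are not estimates for this trial.

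**The case against.** The strongest reply is that the protocol never says in terms that 48-hour MRI will be compared with history. Section 10.1 names neither MRI nor 48 hours. Where a historical use is spelled out (4.9.3 and 8.5.4.3), it is Bayley III converted to Bayley II scores. Where the purpose of the 48-hour scan is spelled out, it is concurrent: section 2.3 refers to both arms of the study, and 4.4.2 to Xenon plus cooling against cooling alone. Which variables go into a supplementary table is often settled in the SAP, which is not at hand. This narrows the point but does not remove it, because 10.1 itself commits to the same variables and makes no exception.

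Three stronger readings are tempting, and the documents do not support them.

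- A reader might infer that the historical 48-hour scans must over-represent severe injury. The protocol does not say how many of the 45 were scanned or why. Routine care is the natural reading of how they are described, but it is not stated. Sections 4.9.1 and 8.5.4.1 even list MRI at about 48 hours among routine investigations, which sits badly with the specific statements in 2.3, 4.4.1 and 4.4.2.
- A reader might infer a false Xenon benefit. The shift would appear in both arms. The randomised cooling arm of 26, reported alongside, would reveal it, and the plan is descriptive with no decision resting on this comparison.
- A reader might take 48-hour ascertainment in the trial as complete for every biomarker. In the protocol summary, item xv of the tertiary objectives limits spectroscopy to some infants, depending on availability of the 3 Tesla scanner, whereas 4.9.1 item 4 includes spectroscopy in the scan. NAA may therefore be incomplete in the trial as well.

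**Conclusion.** The concern holds in conditional form. As written, section 10.1 admits a comparison of 48-hour MRI variables between fully scanned trial arms and a historical group in which, under the routine practice described, only infants causing concern were scanned. If the 45 were managed that way, their scans would over-represent severe injury and both trial arms would look better against them.

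This rests on two assumptions: that the 45 were scanned under routine practice, and that the stated reasons for scanning made more severely injured infants likelier to be scanned. The size cannot be computed from the protocol, so no percentage-point bias should be quoted as a finding.

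The reach is one secondary endpoint in a supplementary descriptive comparison. This mechanism does not affect the randomised comparison, the 18-month Bayley endpoint or the routine 7-10 day MRI. Severity is minor.

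**What to change.** Add one sentence to section 10.1: MRI lesions and biomarkers from the scan at about 48 hours are compared only between the two randomised arms, and the historical MRI comparison is limited to the routine scan at about 7-10 days, which all cooled infants receive.

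A broader rule, using history only for variables recorded in all 45 infants on the same schedule, should not be adopted. At the 10.3% mortality given in sections 4.4.2 and 9.3.2, about 45 × 0.103 = 4.6 of the 45 would be expected to have died, so an 18-month Bayley could not exist for all of them, and the historical Bayley comparison that the protocol plans would be lost. The rule could also exclude the later MRI, since routine scans fall at 7-10 days and trial scans around day 7.

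The cost is one sentence and the loss of a historical 48-hour MRI comparison that could not be interpreted as matters stand.

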A second study (CoolXenon2) has also been successfully undertaken. This study initially was for 24 babies, 12 in each group. One main aim was to establish if we could recruit sufficient neonates within the 5h time limit from birth to Xenon. During this period, when Xe was started only after arrival in Bristol, we lost approximately 40% of potential recruits due to not being able to meet this ambitious time limit. After starting to run the Xe delivery system in the dedicated retrieval ambulance, we applied for an extension to the CoolXe2 study to evaluate the impact on recruitment this would have (8 additional patients, 4 per group) and from that point we have had no missed recruitment due to the 5h time interval.

The CoolXenon2 study revealed an unknown and unforeseen effect of Xenon; Xenon in itself depresses the aEEG trace during delivery which means it is unreliable as an early outcome predictor until the treatment has finished which will for most infants say ≥ 25 h of age (5h old when starting xe +18h treatment + at least 1h recovery). We observed that Xenon depresses seizure activity *per se* (SPR abstract 2013, Appendix 4) and we observed that if Xenon was stopped very fast

Neonatal Xenon Breathing Device: CoolXenon3 Study	Protocol	CI/2013/4414
	Version	Issue 2, Revision 3
	Issue Date	18 Sept 2019
	Page	20 of 79

seizures could occur on stopping Xenon. This means that there is a period where “time to recovery of normal trace” may or may not be affected by Xenon. These data illustrate the importance of examining a small dataset like CoolXenon2 when a new treatment is administered. This means that when analysed the traditional way, aEEG is not reliable as an outcome predictor during the whole of the Xenon administration periods and a few hours afterwards. Since we cannot quantify the aEEG response we do not have a validated early outcome predictor from which we can make a power calculation.

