3.1 Primary Objective

Our hypothesis is that the Bayley Scales of Infant and Toddler Development (Bayley III) scores at 18m of age will show a trend towards an enhanced neuroprotective effect of the Xenon-cooling combination over cooling alone.

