4.1.1 St Michael's hospital standard inclusion criteria for cooling

Standard Hypothermia Treatment Criteria for 72 hrs of cooling — all of criteria A, B and C.

A: *Infants ≥ 36.0 weeks gestation (estimated or clinical assessment) with at least ONE of the following:*

- i. Apgar score of ≤5 at ten (10) minutes after birth
- ii. Continued need for resuscitation, including tracheal or mask ventilation, at ten minutes after birth
- iii. Acidosis defined as either umbilical cord pH or any arterial, venous or capillary pH within 60 minutes of birth less < 7.00
- iv. Base deficit ≥16 mmol/L in umbilical cord blood sample or any blood sample within 60 minutes of birth (arterial or venous blood). If the infant meets criterion A then assess for neurological abnormality using criterion B and C (by trained personnel):

B: *Moderate or severe encephalopathy as evidenced by any of the following:*

Neonatal Xenon Breathing Device: CoolXenon3 Study	Protocol	CI/2013/4414
	Version	Issue 2, Revision 3
	Issue Date	18 Sept 2019
	Page	23 of 79

- i. Altered state of consciousness (reduced or absent responses or pathological irritability and hyper responsive and at least ONE or more of the following:
 - ii. Hypotonia
 - iii. Abnormal reflexes including oculomotor or pupillary abnormalities
 - iv. Absent or weak suck
 - v. Clinical seizures, as recorded by trained personnel

AND

C: At least 30 minutes duration of amplitude-integrated electroencephalography (aEEG) recording that shows abnormal background aEEG activity. The decision to cool is based on the worst 30 min section of the aEEG, not the best³⁸ or seizures (clinical or electrical) thus meeting ONE of the following:

- i. Normal background with some (> 5 min) electrical seizure activity
- ii. Moderately abnormal activity (upper margin of trace >10µV and lower margin <5µV)
- iii. Suppressed activity (upper margin of trace <10µV and lower margin of trace <5µV)
- iv. Definite seizure activity

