4.3 Randomisation

The babies entered into the study will be randomised into two groups on a 1:1 basis. Randomisation will be via sealed opaque envelopes containing details of treatment allocation and [an] identifying adhesive label(s) to be attached to the CRF binder. Neonates meeting all the entry criteria can be included. In this study early randomisation before 5h of age is paramount. The maximum target delay before starting cooling is before 3h of age and for Xenon this value is 5h of age. These are maximum delay values however, so consent and randomisation need to take place as early as possible.

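### Section 10.1 plans descriptive comparison of two groups of 26 and makes no use of the pre-Xenon aEEG background recorded in every infant; one prespecified adjusted estimate would be worth adding

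*Protocol*

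**What the plan says.** The primary outcome is the 18-month Bayley examination: "The Bayley clinical neurodevelopmental examination at 18months of age is the primary outcome measure" (2.3). The hypothesis in 3.1 is of "a trend towards an enhanced neuroprotective effect of the Xenon-cooling combination over cooling alone". Section 10.1 gives the whole stated analysis. "Sample size is 26 infants in each group"; "Data presentation will include descriptive statistics only"; results are compared between the two arms and with 45 historical cooled infants; and "Differences between the groups will be estimated". No model, covariate or interval is mentioned. The comparison is not called unadjusted, and adjustment is not ruled out.

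Criterion C in 4.1.1 (repeated in 6.2.1) is mandatory. It requires at least 30 minutes of "recording that shows abnormal background aEEG activity", or seizures, and the decision to cool rests on the worst 30-minute section. Endpoint 12 in 3.4 also records the aEEG background before Xenon. Section 4.3 says "Randomisation will be via sealed opaque envelopes containing details of treatment allocation", with 1:1 allocation; neither 4.3 nor 7.0 describes stratification or any other balancing factor.

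**The concern.** With 26 infants per arm, the arms can easily differ by chance in how severely affected the infants were at entry. A raw Bayley difference then mixes that difference with any effect of Xenon. The information needed to separate them is collected in every infant before treatment, but nothing stated in the design or the analysis uses it.

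The word restricting presentation to descriptive statistics takes this beyond a detail left to a statistical analysis plan. A covariate-adjusted difference is not a descriptive statistic, so a later plan that adjusted would sit awkwardly with 10.1. There is also a practical hazard. The aEEG measure that section 1.0 singles out as the best early predictor is time to recovery of a normal trace. That is measured after randomisation, and 2.3 reports that Xenon itself depresses the trace. If the covariate is not named in advance, the wrong aEEG variable could be chosen later.

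**Working it through.** **No planned figure to reproduce.** The protocol gives no SD, target difference, alpha or power for the 26 per arm. Section 2.3 says "Since we cannot quantify the aEEG response we do not have a validated early outcome predictor from which we can make a power calculation".

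**Inputs from the protocol.** 26 per arm (10.1). Mortality 10.3% (4.4.2), so 26 × (1 − 0.103) = 23.3, taken as 23 survivors per arm with a Bayley score. In the 14-infant feasibility study (Appendix A3), 90% had burst suppression before cooling.

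**Assumptions.** Bayley SD 15 points; share of Bayley variance explained by entry aEEG (R²) from 0 to 0.3; proportion with suppressed aEEG at entry from 30% to 90%. The protocol gives none of these for this trial. The ratios of half-widths below do not depend on the SD.

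**Chance imbalance at entry.** Treat the number with suppressed aEEG in each arm as binomial(26, p). The exact probability that the arms differ by 5 or more such infants is:

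| p | Probability |
|---|---|
| 0.3 | 0.17 |
| 0.4 | 0.20 |
| 0.5 | 0.21 |
| 0.9 | 0.04 |

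For scale, if suppressed infants scored 15 points lower (assumption), a gap of 5 in 26 would move the raw difference by 5/26 × 15 = 2.9 points.

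**Precision, 23 per arm.** Unadjusted half-width = t(44) × SD × √(2/n) = 2.015 × 15 × √(2/23) = 2.015 × 4.423 = 8.91.

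With one binary covariate and its expected chance imbalance, half-width = t(43) × SD × √(1 − R²) × √(2/n) × √(1 + 1/(2n − 4)). Here t(43) = 2.017 and the last factor is √(1 + 1/42) = 1.012.

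| R² | Half-width | Ratio to 8.91 |
|---|---|---|
| 0 | 9.03 | 1.01 |
| 0.1 | 8.56 | 0.96 |
| 0.2 | 8.07 | 0.91 |
| 0.3 | 7.55 | 0.85 |

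Adjustment breaks even at R² of about 0.02.

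**If most infants share one pattern.** For a 15-point effect of grade and residual SD 15, R² = 225p(1 − p) / [225p(1 − p) + 225]. At p = 0.5 this is 56.25/281.25 = 0.20; at p = 0.9 it is 20.25/245.25 = 0.08. At R² = 0.08 the interval narrows by only about 3%.

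**Why one term.** The four criterion C routes (three indicators) plus hospital make four terms. The variance factor becomes 1 + 4/(46 − 4 − 3) = 1.103, and t(40) = 2.021. At R² = 0.1 the half-width is 2.021 × 4.423 × √0.9 × √1.103 = 8.91, the same as unadjusted. The extra terms use up the gain.

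**The case against.** A reader might infer that the protocol fixes an unadjusted comparison. It does not. An adjusted difference is also an estimated difference, the descriptive-only sentence speaks of presentation, and covariates are commonly chosen in a statistical analysis plan, which is not shown here. This stands in part: a raw comparison is the natural reading of 10.1, but it remains an inference.

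A reader might also infer that the result would be biased. It would not. Randomisation makes the unadjusted difference unbiased over repeated allocations, and its interval already allows for chance imbalance. For a pilot that looks for a trend, adjustment is good practice, not the repair of a fault. That stands.

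The size of the gain is uncertain. The protocol gives no prognostic strength for entry aEEG; its predictive claims are for time to recovery. The only entry distribution it gives suggests that infants may cluster in one pattern, although that study had 14 infants and burst suppression is not a category of criterion C. This stands too, and is why the ranges above run down to no gain.

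Finally, criterion C is an entry screen, not a severity scale. Its four routes mix background voltage with seizures and can overlap. It therefore cannot be entered as it is; a simple coding of the background is needed.

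**Conclusion.** The point holds as a recommendation. Section 10.1, followed as written, compares two groups of 26 descriptively and uses no baseline severity, although pre-Xenon aEEG background is recorded in every infant and no balancing in randomisation is described. Under the assumed SD of 15 and with 23 survivors per arm, one binary aEEG term takes the half-width from 8.9 to between 8.6 and 7.6 points for R² of 0.1 to 0.3. It costs about 1% if entry aEEG is not prognostic and gains little if nearly all infants share one pattern. The chance of a gap of 5 or more suppressed infants is 17–21% if 30–50% are suppressed, but about 4% at 90%. The documents do not support calling this an error, a bias or a known loss of precision. Neither estimate deals with infants who die before the Bayley examination.

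**What to change.** Add to 10.1 that, besides the unadjusted Bayley difference, the difference will be estimated by linear regression on treatment and one binary term for pre-Xenon aEEG background. Code that term as suppressed or not suppressed, using the suppressed definition in criterion C and the worst 30-minute entry section. Show both differences with 95% intervals. State that no aEEG recorded during or after Xenon, including time to recovery, will be used as a covariate. Amend the descriptive-only sentence so that it does not conflict with this. If a statistical analysis plan already specifies adjustment, bring 10.1 into line with it.

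The cost is a sentence or two of text and a coding rule for the entry trace, fixed before outcome data are seen. No new measurement and no additional infants are needed.
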